Furthermore, two recent randomized controlled trials evaluating preterm delivery prevention programmes that included weekly or bi-weekly visits, cervical examinations and education with a total sample size close to 3,300 women did not demonstrate a protective effect for preterm delivery or LBW (Goldenberg, 1990; Collaborative Group, 1993).

Conversely, it has been suggested that simpler, "less technologically-oriented" prenatal care would be less demanding to women and the health system, without compromising pregnancy outcome. There have been three attempts to evaluate a simplified system

(Zimbabwe, Holland, and Scotland). A model being tested in Scotland (Greater Glasgow Health Board, 1991), approaches this goal by proposing "only seven visits for those in the lowest risk category, with more emphasis on "psychosocial midwifery care".

By means of a randomized controlled trial, WHO, in collaboration with research institutions in 4 developing countries, proposes to evaluate whether a programme of antenatal care which emphasizes essential elements of care that have been demonstrated to affect pregnancy outcome is more effective than a traditional programme of antenatal care in preventing maternal and fetal morbidity and mortality. The 4 study sites include Rosario, Argentina, Havana, Cuba, Jeddha, Saudi Arabia and Khon Kaen, Thailand. The relative cost of the two programmes, health care providers' and patients' satisfaction will also be assessed by the other 2 components of the study.

The trial includes random allocation of antenatal care clinics in each of the 4 sites to either a traditional programme of care (i.e. the one currently in place) or to a rationally designed programme focusing on the essential elements of proven efficacy. Women attending either programme of prenatal care will receive their intrapartum care in hospitals.

3. OBJECTIVES

3.1 Goal

The goal of the whole project is to define and evaluate a new model of antenatal care that includes only those components which have been demonstrated to be effective in improving maternal and perinatal outcomes. The choice of each process and outcome variable is therefore made on the assumption that antenatal care will causally affect it.

3.2 Objectives

The objectives of the whole project are :

- To conduct a multicentre, multinational controlled trial comparing two models of antenatal care;
- To establish the relative merits of each model;
- To test whether the proposed new model is more effective than the traditional multivisit model with regard to maternal morbidity and perinatal morbidity and mortality, cost and satisfaction.

The objective of the study at Khon Kaen, Thailand is to participate in the high quality multicentre, multinational randomized controlled trial comparing two models of antenatal care. It was expected to contribute about 6,000 subjects for the whole project.

4. METHODOLOGY

4.1 Introduction

To test the hypothesis that a new model of antenatal care is more efficient than the traditional package with regard to specified maternal and perinatal end points, large numbers of pregnant women must be recruited and the study must include several physicians, midwives and other health care personnel, and have a multicentre design. Compliance with the assigned programme by care providers and receivers is crucial to implementation of the trial.

4.2 Study Design

A randomized controlled trial is necessary for the evaluation of the effect of antenatal care on pregnancy outcome specifically to control for bias in patient selection, as has occurred in most of the observational studies. Women delivering preterm infants have less "gestational time" for more prenatal visits, thus making the association between prenatal care and prematurity stronger. Conversely, late initiators of prenatal care have fewer preterm newborns because they are still pregnant after 36 weeks, thereby weakening the effect. Women with known medical complications tend to attend early and have more visits but also have more preterm/IUGR infants, producing the U-shaped curve of the association (more care, more preterm/IUGR). Finally, healthy well-educated women who have very low risk for preterm-IUGR will also attend early, have many visits and make the association stronger. All these recognized selection biases, as well as those presently ignored, can only be controlled by a large randomized controlled study design.

The study is a large, multiclinic, multisite, randomized controlled trial of two different models of antenatal care; a new model of care will be compared with the traditional recommended model as it is presently implemented in the selected sites. Maternal, fetal, perinatal, cost and satisfaction end-points will be compared. The trial are conducted in four sites worldwide; each study site will include between ten and twelve antenatal care clinics

[figure not shown]
(clusters). All women attending each clinic will be included in the assessment of the clinic end-points and will be registered on their first antenatal visit and followed until discharge from the hospital post-partum. Deliveries from all ANC clinics (intervention and control) in a particular study site should occur at the selected medical facilities (Figure 1). Antenatal care clinics (cluster randomization), not individual women, will be randomized to the two arms of the study. Randomization will be stratified within each geographic study site by the size of the patient population enrolled in each clinic or cluster (large, medium and small clusters).

4.2.1 Randomized controlled trial

When testing the effect of new drugs or procedures by comparing against old treatment or placebo, patients are usually individually randomly allocated to one or the other alternative treatment modality. Statistical comparison is then made between patients allocated to each of the two (or more) treatment groups. In this design, precautions are taken to avoid bias favoring one or the other treatment, and against the possibility that care providers and test subjects, consciously or unconsciously, violate procedural rules in order to affect the outcome. This is often achieved by "blinding" the study patients and in some instances also the researcher ("double-blinding").

Obviously, the two models of antenatal care cannot be "blinded." Given prior information, it will immediately be clear to participants (both care providers and care receivers) to which arm of the trial each belongs. It is also obvious that care providers, as a condition for participation, must be given full information about both antenatal care programmes before randomization. Ideally, the two models of antenatal care should be tested by random allocation of study subjects, which would require detailed information before consent is given. Full information with free choice of participation implies that those not willing to participate will receive an alternative form of care, which may be the traditional, the new model or even a combination of the two. This invites new problems which would invalidate the trial.

Figure 1: Trial Organization

Within the individual study site, there would also be confusion regarding the content of each visit of the individual woman, and there would be the obvious risk that the two systems may ultimately fuse into one ("contamination") before the trial is completed (Kramer, 1989). To avoid these problems, which would, in the end, invalidate the trial, we propose to randomize by unit (cluster randomization). The ethical questions this raises will be discussed in Section 4.15.

4.2.2 Randomization by unit

The study units will be antenatal care clinics serving well-defined geographic areas. Randomization by unit (or clusters) is an excellent methodological strategy in evaluating the effect of global changes in mode of practice. Detailed review of the properties and limitations of design have been published elsewhere (Donner and Klar, 1994; Buch and Donner, 1982). For example, a very important large randomized trial of vitamin A supplementation conducted in northern Ghana using geographical areas as randomization units (clusters), was recently completed and published (Ghana VAST Study Team, 1993). Cluster randomization has also been used for the evaluation of a community intervention of growth monitoring in South India, in which six pairs of villages were formed and randomization was conducted within them (George, 1993).

These recent examples, along with previous large studies also using cluster (clinics or health care providers) randomization in the perinatal field (Grant, 1989; Bullough, 1989), strongly support the usefulness of this type of study design for the evaluation of health care strategies.

In the case of the present study the two main reasons for choosing clusters as units of randomization are: to reduce treatment contamination and for administrative and logistic convenience in the implementation of the intervention. As it is possible that analyses using women as units may be performed, we have accounted for the between cluster variation in the calculation of sample size and study power.

The population attending the clinics in each country should be similar with regard to sociodemographic factors, and have study-relevant mortality and morbidity rates in the same order of magnitude. An antenatal care programme following traditional standards delivered through the public sector should be already available to pregnant women. Furthermore, all participants should plan to deliver in hospitals, not least for practical recording purposes. To obtain a reliable answer within a reasonable period of time, there will be several antenatal care clinics (clusters) for comparison, stratified by study site and cluster size. Each clinic or cluster will be expected to manage between 450 and 500 antenatal care patients during the study period. However, as it is more important the number of clusters than the size of them it is possible that for logistic reasons smaller antenatal care clusters could be accepted (about 300 antenatal care patients per cluster).

Each site considered for the study should be able to:

1. produce reliable data on the primary maternal and newborn outcomes in the city or region.
2. Provide written evidence that the new programme will be acceptable to local authorities and physicians.
3. Recruit between 10 and 12 antenatal clinics from the public sector (see criteria for clinic selection) in a geographically identified region.
4. Have a common formal system of perinatal data collection and maternal cards already in place.
5. Have an effective system for referral of high-risk women from the clinics to a tertiary level hospital.

6. Have a regional epidemiological research unit with field research experience; previous participation of this unit in multicentre studies is required. Computer facilities at the research unit-hospital or university-should be available to the study group.
7. Country should allow data (multicentre trial) to be sent to the central analysis centre (Geneva) and to be pooled with those from the other centres.

The criteria for each antenatal care clinic to be included for randomization is as follows :

1. Each antenatal care clinic (the randomization unit) to be included should be able to provide between 300 and 500 new patients in a period not longer than 18 months.
2. Intervention and control clinics will be in the same geographical area.
3. "Same geographical area" relates to same city or district; the ideal situation will be clinics serving different neighbourhoods of a city or areas of a rural province.
4. All women from these antenatal care clinics should deliver at hospitals.
5. The hospitals should also be the referral place for all high-risk patients.
6. The clinics should be part of a public (or semi-public) antenatal care system. Military hospitals or social security institutions are also eligible. The study will not include clinics where direct fee-for-services payments are required.
7. All clinics should have an antenatal care system already in place with norms and predefined activities which are followed.

8. The clinics should be able to implement new simple tests or activities as required by the protocol. Funds for these new activities should be provided by the institution(s), as they will be for direct patient care only. These few new activities will replace several presently implemented ones.
9. The clinics should have an already working and economically supported minimum staff required for patient care by the protocol.

4.2.3 Limitations of the study design

It is possible that the outcome of women attending the new programme will be altered by the introduction of a new system, regardless of its components and of any differential effects of the two treatments. Furthermore, it is also possible that outcomes will improve in the control group by means of a better utilization of resources available in the traditional system, as well as by more active participation of nurses and physicians. Patients entered into a trial tend to receive more careful management in all aspects of care. Finally, although effort will be made to maintain a blind status for delivery and neonatal care providers, it is likely that they will know the treatment status and perhaps act differently based on their belief of antenatal care. However, most of the selected outcomes are little influenced by intrapartum care and it is expected that this effect will be minimum. Nevertheless, the study will attempt to evaluate this effect, if present, by the following mechanisms:

1. During the preparatory phase of the study, information were collected at the cluster level in all sites on the main outcome variables and a selected number of process variables. This baseline information will be compared with data obtained during the trial (before and after analysis). Most likely, available baseline information will be at hospital or area level, and specific clinic data will be obtained during the preparatory phase only.

2. Information on intrapartum events partially unrelated to antepartum care, e.g. emergency cesarean section, forceps delivery, were collected during the preparatory phase. Comparisons will be made between the two treatment groups; it is expected that no differences will be present during the preparatory and study periods.
3. Trends will be observed in perinatal events at all participating hospitals irrespective of whether patients are participating in the antenatal care study.

4.2.4 Discontinuation of study units or patients

The complete study will be discontinued or stopped as decided by the Data and Safety Monitoring Committee and the Steering Committee if the "experimental group" is having overall a worse outcome, as defined in the "Stopping Rules". Based on sample size calculations, an increase in the intervention group, of more than 25% from the control group in any of the primary outcomes will be specifically analysed by the Data and Safety Monitoring Committee.

Discontinuation of a study cluster is an important problem and steps will be taken to reduce the likelihood of this before the initiation of the study. There are two elements that can contribute to the need for discontinuation:

- (a) very low recruitment rate (< 30% of the expected number of patients in a clinic/s).
- (b) lack of compliance in the application of the new antenatal care programme by clinic personnel after initial acceptance.

To prevent the first problem, a retrospective review of several years' trend in patient attendance at the clinic was studied. Only those clinics with stable and adequate number of patients initiating antenatal care are included. To prevent the second problem, meetings were

conducted with the staff of all clinics to evaluate their willingness to participate in the trial if they are randomized to the intervention group, and a "dry run" of the trial was conducted after the preparatory workshops for a period of one month in some of the clinics allocated to the new programme in order to detect problems and reaction of personnel. Only after this period, and upon general agreement with the intervention, would the new programme be considered ready to start.

During the course of the study, and only under extreme circumstances (it could lead to major bias), the following criteria could be used for discontinuation of a study unit:

Lack of adherence to data collection principles;

- major organization changes which make continuation impossible;
- rate of recruitment less than 30% goal for at least 6 months;
- more than 20% of eligible patients refuse to participate in the study and choose other clinics.

Any excluded clinic/s (cluster/s) will be included in the final analysis in the group to which it was randomized up to the time of the discontinuation, regardless of the completeness of the programme implemented. All women included up to discontinuation will be followed up until delivery and included in the analysis.

Patients will not be discontinued from the new antenatal programme. If some women refuse to continue, they will be offered the traditional antenatal care at the same clinic or referred to an alternative clinic if it is located nearby and does not represent any inconvenience for the patient. In both situations, patients will be included in the analyses as part of the cluster where they were originally enrolled.

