4.2.5 Eligibility of patients

All patients attending the first prenatal visit at the study clusters after the date of the start of the study, regardless of their history or medical condition, will be included in the study, and their medical record will be used in the analyses. Those enrolled for prenatal care at the control clinics will follow the standard procedure and be referred for delivery at the identified hospitals. Women enrolled in the new (intervention) programme clinics receive the new prenatal care programme and/or standard treatments of medical care if needed at any time during pregnancy. All patients will be considered for the analysis as part of the intervention population.

If a women has more than one pregnancy during the study period in one of the antenatal care clinics of the study, only the first pregnancy of that women will be included in the analysis.

Efforts will be made to locate those women who registered for antenatal care but had an abortion. Those women for whom information is not available for pregnancy outcome or termination will be treated as lost to follow-up.

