- (d) Those study sites that currently offer activities know to be useful (e.g. alpha fetoprotein screening), but are not recommended in the basic package for logistic, economical or legal reasons, will continue performing those tests or procedures on all patients, regardless of randomization status.
- (e) There are currently large randomized controlled trials evaluating alternative forms of care for eclampsia or preventive interventions such as low-dose aspirin and calcium supplementation. In the event that results are available during the trial, the recommendations will be included in the antenatal care programme of both arms of the trial.

In reference to the informed consent, we are proposing that it be requested only from patients attending the antenatal clinics randomized to the new package (Hemminki, 1989; Zelen, 1979). Women attending the control clinics will receive the "best standard treatment" as presently offered in those clinics. Furthermore, because of the cluster allocation, informed consent of patients in the control group is not required, because data will be used no differently from the routine use of aggregate data by clinical departments for analysis of outcome information (Zelen, 1992).

Patients refusing to participate in the new programme will be offered the routine care at the same clinic or referred to the closest prenatal care clinic not included in the control group, but which offers the standard antenatal care for public institutions if the latter option is more convenient to the mother. Nevertheless, these patients will be included during the analysis in

the intervention clinics as originally randomized. The percentage of patients refusing the new programme will be used as process variables during the analysis. "Treatment" groups will continue with the same "treatment" to new patients during the follow-up of the last cohort of women enrolled in the study (about 6 months).

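### One of the four in-trial grounds for discontinuing a clinic, refusal by more than 20% of eligible women, can be met only by intervention clinics, so using it would cut enrolment short in one arm alone

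*Protocol*

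**What the plan says.** Section 4.2.4 deals with discontinuing a clinic in two steps.

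It first names two things that can create the need: recruitment below 30% of expectation, and "lack of compliance in the application of the new antenatal care programme by clinic personnel after initial acceptance". For each it describes steps taken before the trial: a review of attendance trends for the former, staff meetings and a one-month dry run for the latter.

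It then gives the grounds that may be used while the trial is running, "only under extreme circumstances (it could lead to major bias"). There are four: poor adherence to data collection, major organisational change, "rate of recruitment less than 30% goal for at least 6 months", and "more than 20% of eligible patients refuse to participate in the study and choose other clinics". Programme non-compliance is not among them.

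A discontinued clinic stays in its randomised group with the data gathered up to the stop: "All women included up to discontinuation will be followed up until delivery and included in the analysis". Nothing is said about women who first attend after the stop.

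Section 4.15 states that consent is to be "requested only from patients attending the antenatal clinics randomized to the new package". It offers refusers routine care at the same clinic or another one, keeps them in the analysis as randomised, and makes the refusal percentage a process variable. The section on implementation in Khon Kaen confirms that verbal consent was taken only in the six intervention hospitals. It adds that non-consenting women were asked to attend elsewhere.

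**The concern.** A rule for closing a randomised unit should be capable of applying to either arm. The refusal ground is not, because a woman who is never asked for consent cannot refuse. It also depends on a property of the intervention: refusal measures how acceptable the new model is, and the plan itself treats it as a process variable. The same quantity is therefore both measured and allowed to end a clinic's enrolment.

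At stake is the balance that randomising clinics was meant to give. If an intervention clinic with poor acceptance stops early, its later attenders never enter the trial, while the control clinics in its stratum recruit to the end. Following the women already enrolled does not replace those who are missing.

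The two lists in 4.2.4 also leave unclear whether poor application of the new programme is a ground for closing a clinic. If it is, it too can occur only in the intervention arm.

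**Working it through.** **1. Which arm can meet each operative ground?**

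| Ground (4.2.4, operative list) | Intervention | Control |
|---|---|---|
| Poor adherence to data collection | yes | yes |
| Major organisational change | yes | yes |
| Recruitment under 30% of goal for 6 months | yes | yes |
| More than 20% refuse and go elsewhere | yes | no, consent is not sought (4.15) |

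One of four is arm-specific. Programme non-compliance appears only in the preceding list and has no stated operative status.

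**2. Women lost if one Khon Kaen intervention clinic stops halfway** (Table 16: 3,449 intervention women; largest clinic 1,064, smallest 219).
- Largest: 1,064 / 2 = 532; 532 / 3,449 = 15.4%.
- Smallest: 219 / 2 ≈ 110; 110 / 3,449 = 3.2%.
- The comparison pools four sites with about 20,000 women, taken here as 10,000 per arm: 110 / 10,000 = 1.1% and 532 / 10,000 = 5.3%.

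**3. Power.** The plan's own figure comes first: Table 7(c), odds ratio 1.18, 90% power, two-sided 0.05, control rates 0.07, 0.09, 0.11 and 0.13, intracluster correlation ρ = 0.00065, clinic size m = 450. A stratified two-proportion sample size with equal strata and 1:1 allocation gives 16,080 at ρ = 0 (stated: 16,085). The design effect is 1 + (450 − 1) × 0.00065 = 1.29185, and 16,080 × 1.29185 = 20,773 (stated: 20,780). The figure reproduces.

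Next, take 24 clinics of 450 per arm (10,800 women), 10% against 11.6%, and divide the numbers by the design effect. The number of clinics closed is an assumption.

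| Intervention clinics closed | Intervention women | Power, ρ = 0.00065 | Power, ρ = 0.002 |
|---|---|---|---|
| none | 10,800 | 91.2% | 78.1% |
| 2 halfway | 10,800 − 2 × 225 = 10,350 | 90.7% | 77.3% |
| 6 halfway | 10,800 − 6 × 225 = 9,450 | 89.3% | 75.3% |
| 6 entirely | 10,800 − 6 × 450 = 8,100 | 86.7% | 71.9% |

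Closing a few clinics costs little power. The issue is who is missing.

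**4. Direction.** If d women with rate p are removed from an arm of N women with mean rate P, the mean moves by −d(p − P)/(N − d). As an illustration with no treatment effect, apply the low birth weight rates of Table 1 to the Table 16 numbers of the six intervention clinics:

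P = (1,064 × 8.0 + 759 × 5.6 + 594 × 9.1 + 493 × 9.4 + 320 × 8.0 + 219 × 4.4) / 3,449 = 7.63%.

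- Stopping Phol (9.1%) halfway: −297 × (9.1 − 7.63) / 3,152 = −0.14 percentage points.
- Stopping Banphai (5.6%) halfway: −379.5 × (5.6 − 7.63) / 3,069.5 = +0.25 percentage points.

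These are the extremes among the six. The shift can go either way, depending on which clinic stops. The illustration covers baseline risk only. It says nothing about whether the effect of the new model differs where acceptance is low.

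**5. Was the rule used in Khon Kaen?** All twelve clinics appear in Table 16, with 3,449 intervention and 3,316 control women. Five of the six intervention clinics recruited more than their annual figure in Table 1. The sixth, Chumpae, reached 1,064 / 1,330 = 80%, but two control clinics also fell short: Kranuan 859 / 1,025 = 84% and Manjakiri 342 / 466 = 73%. The table points to no closure.

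**The case against.** The best defence is that the rule is hedged. It is optional, confined to extreme circumstances, and accompanied by the protocol's own warning of bias. It requires women both to refuse and to go elsewhere, whereas 4.2.4 and 4.15 offer refusers traditional care at the same clinic. Women already enrolled are kept in the randomised arm however incompletely the programme was applied. All of this is true and makes use of the rule unlikely, but it does not make the rule symmetric or recover later attenders. Khon Kaen practice, which sent non-consenting women elsewhere, also made the second half of the condition easier to meet.

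A second objection has weight. Section 4.8.1 requires the new programme to show no increase in the primary outcomes. Continued enrolment in clinics that no longer deliver it draws the arms together and makes that conclusion easier to reach. This is the usual consequence of intention to treat, which 4.2.4 already accepts, and it should be stated when results are interpreted.

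A reader might infer more than the text supports:
- That two operative grounds are one-sided. Non-compliance is named only as a contributing element, followed by preventive steps, so its status is unclear.
- That the trial would compare well-performing intervention clinics with all control clinics, to the advantage of the new model. A stopped clinic loses weight but is not removed, and nothing in the protocol shows that outcomes are worse where acceptance is low.
- That 4.2.5 is contradicted where it says that women making a first visit at a study cluster, "regardless of their history or medical condition, will be included in the study, and their medical record will be used in the analyses". That rule concerns clinics still in the study.

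**Conclusion.** The point holds in limited form. One of the four operative grounds can occur only in the intervention arm and is tied to acceptance of the new model. Its use would truncate enrolment on one side only. The result would be a possible selection bias of uncertain direction. A bias favouring the new model is plausible but not shown.

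The loss from one clinic stopped halfway is 3% to 15% of the Khon Kaen intervention arm. The pooled comparison is the relevant one, and there it is about 1% to 5%, assuming 10,000 per arm. Power falls from 91.2% to 89.3% even if six of 24 intervention clinics stop halfway, at the plan's intracluster correlation. Nothing in the Khon Kaen data suggests that a clinic was dropped, and the report does not show the other three sites. Separately, the two lists in 4.2.4 disagree on programme non-compliance and must be reconciled.

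**What to change.** In 4.2.4:
- Remove refusal above 20% as a ground for ending a clinic's enrolment, and state that non-compliance with the new programme is not one either. This reconciles the two lists.
- State that a clinic with high refusal or poor application of the programme keeps registering all attenders and completing Summary forms to the end of recruitment, and is analysed as randomised.
- Report refusal and non-compliance by clinic as process measures. Section 4.15 already does this for refusal.
- Keep only grounds that can arise in either arm, such as organisational change that makes continuation impossible.

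Khon Kaen recruitment is complete, so at this site the change affects reporting only. The four-site report should list any clinic discontinued at any site, with its arm and the criterion used.

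The change concerns registration and analysis and prescribes no care. It costs protocol wording plus continued form completion at any clinic that would otherwise have stopped. The downside is some dilution of the estimated difference, to be acknowledged if the conclusion is that the outcomes did not increase.
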